Pre-biopsy High Resolution Anoscopy Finding	Minimally required procedure
No lesion	Punch biopsy and photography; biopsy should be collected from within the approximate original boundaries of the study entry HSIL as proximal as possible to the original biopsy site which was previously determined to be HSIL by the PAC. New lesions or lesions that did not qualify at baseline should be biopsied at evaluation.
Single lesion (which was also present at baseline)	Punch biopsy and photography; biopsy should be collected within the boundaries of the original lesion and from the area most suspicious for advanced disease within the lesion by clinical exam. New lesions or lesions that did not qualify at baseline should be biopsied at evaluation.
Multiple lesions	Punch biopsies and photography; biopsy should be collected from the same lesions diagnosed as HSIL from study entry and from the area most suspicious for advanced disease within the lesion by clinical exam. New lesions or lesions that did not qualify at baseline should be biopsied at evaluation.

If HSIL is diagnosed in any Week 36 biopsy, but there is a reduction in the number of intra-anal and/or peri-anal lesion(s), reduction in peri-anal lesion(s) size or no change in peri-anal lesion(s) size from baseline (defined by Subgroup C), the Investigator has the option to administer a 4th dose of VGX-3100 at Week 40, and the subject will continue on the study to have HRA and biopsy at Week 64 of all lesions (qualifying and any other visible), i.e. the second efficacy checkpoint. Alternatively, the Investigator may instead choose to treat the subject with standard of care treatment (i.e. electrocautery, ablation, surgical excision), and the subject will continue on the study without further biopsy unless it is part of standard of care.

In the event of worsening anal or anal/peri-anal HSIL at any time during the trial (defined as any increase in lesion(s) area from baseline or worsening of anal or anal/peri-anal HSIL to cancer), the subject may receive standard of care treatment (i.e. electrocautery, ablation, surgical excision) per the Investigator's judgment but will continue on the study through Week 88 with HRA, but without further biopsy unless it is part of the standard of care.

If there is histologic progression to carcinoma, subjects will receive surgical treatment, and be discontinued from study treatment but will continue through Week 88 with HRA, but without further biopsy unless it is part of the standard of care. The event will be reported as an SAE per Section 7.3. If wide excision is required, the sample(s) obtained will be sent to the PAC for evaluation.

Efficacy Assessment:

Screening biopsies will be collected from all intra-anal and/or peri-anal lesion(s) of adequate size (≥ 4 mm). Visible lesion(s) observed during HRA should be large enough to biopsy, but the biopsy (typically 4mm) should not remove the entire lesion in order to allow for continued lesion measurement while on the study.

Given that HPV infection persistence is a critical factor in the clinical progression of HPV-associated anal or anal/peri-anal HSIL and also based upon the findings of the secondary objective of the HPV-003 CIN2/3 proof of concept study, the responder definition for the HPV-203 primary endpoint determination requires both histological regression of anal or anal/peri-anal HSIL and clearance of HPV-16 and/or HPV-18 [1].

Regression of anal or anal/peri-anal HSIL will be determined by histopathologic assessment of intra-anal tissue, utilizing HRA with biopsies. All intra-anal and/or peri-anal lesion(s) of adequate size (≥ 4 mm) will be biopsied at Screening. Once the PAC confirms HSIL at Screening, the Week 36 and 64 biopsies will be obtained from all HSIL site(s) confirmed by the PAC at Screening, unless the Investigator suspects disease progression. In addition to HSIL lesion(s) found at Screening, all visible lesions should have biopsy obtained at Week 64 and samples to be sent to the central pathology lab for PAC review. Tissue samples will be analyzed for evidence of histopathologic regression. Clearance of HPV-16 and/or HPV-18 will be determined using the type specific HPV PCR test on intra-anal and/or peri-anal tissue performed at Screening and Weeks 36 and 64 when applicable.

Intra-anal and/or peri-anal swabs will be collected at Screening, Day 0, and at Weeks 4, 15, 28, 36, 64 and 88 as a less invasive measure for exploratory purposes to determine the presence of HPV-16 and/or -18 as well as other high risk HPV types using HPV testing. Similarly, vaginal, cervical (female subjects), penile (male subjects), and oropharyngeal (OP) rinse samples will be obtained at Day 0, and Weeks 4, 15, 28, 36, 64, and 88 to assess systemic virologic response to treatment.

If after evaluation of the biopsy tissue at Week 36, HSIL remains, but there is a reduction in intra-anal and/or peri-anal lesion(s) number and no increase in peri-anal lesion(s) size from baseline (Subgroup C), the Investigator will have the option to administer a 4th dose of VGX-3100 at Week 40 and the subject will continue on the study with HRA and biopsy at Week 64. Alternatively, the Investigator may choose to treat the subject with standard of care treatment (i.e. electrocautery, ablation, surgical excision), and the subject will continue on the study without further biopsy. If HSIL remains based on the Week 64 biopsy results, the subject will receive standard of care and remain on the study for safety and follow up only.

Immunogenicity Assessment: Humoral and cell mediated immune responses to VGX-3100 may be evaluated in blood samples taken at baseline (both Screening as well as Day 0 prior to dosing) and at Weeks 15, 36, and 88. Intra-anal and/or peri-anal tissue samples may also be analyzed for evidence of proinflammatory and immunosuppressive elements at Week 36 as compared to baseline (Screening), where feasible.

Virologic Assessment: Intra-anal and/or peri-anal swabs will be obtained to characterize HPV infection at Screening, Day 0, and Weeks 4, 15, 28, 36, 64 and 88. Likewise, PCR-based assessment of histological samples will occur at Screening and Weeks 36 and 64.

For testing of non-anal sites, vaginal, cervical (female subjects), penile (male subjects), and oropharyngeal (OP) samples (all subjects) will be obtained to characterize HPV infection at Day 0, and at Weeks 4, 15, 28, 36, 64 and 88.

Safety Assessment: Subjects will be monitored for:

- 1) Local and systemic events for 7 days following each VGX-3100 dose as noted in the Participant Diary Card (PCD).
- 2) All adverse events including SAEs, UADEs, and other unexpected AEs for the duration of the study.

All subjects will be followed to Week 88.

Data Safety & Monitoring Board (DSMB): An independent DSMB will meet quarterly to review safety data and tissue regression and viral clearance results. The DSMB will be charged with advising the Sponsor if there appears to be a safety issue. No formal interim analysis is planned. Refer to Section 3.8 for stopping rule criteria.

Definition of Responder and Non-Responder:

Responder and non-responder definitions (**Table 2 through Table 7**) take into account both histopathologic regression of anal or anal/peri-anal HSIL **and** virologic (HPV-16/18) clearance as measured by intra-anal and/or peri-anal tissue, since HPV persistence is an important factor in the clinical progression of HSIL. Any case of histologically confirmed progression from HPV-16/18 positive anal or anal/peri-anal HSIL to carcinoma according to the PAC is considered a non-responder.

Table 2: Definition of Responder and Non-Responder for Composite Endpoint of Regression and Clearance	
Responder	Non-Responder
No histologic evidence of anal or anal/peri-anal HSIL AND Negative PCR for HPV-16 or HPV-18 in anal lesion tissue AND No non-study treatment of curative intent of intra-anal and/or peri-anal lesions	Histologic evidence of anal or anal/peri-anal HSIL, anal Adenocarcinoma-in-situ (AIS), anal or anal/peri-anal carcinoma OR PCR positive for HPV-16 or HPV-18 in anal lesion tissue OR Any non-study treatment of curative intent of intra-anal and/or peri-anal lesions

Table 3: Definition of Responder and Non-responder for HSIL Regression Endpoint

Responder	Non-Responder
No histologic evidence of anal or anal/peri-anal HSIL 
AND
 No non-study treatment of curative intent of intra-anal and/or peri-anal HSIL	Histologic evidence of anal or anal/peri-anal HSIL or carcinoma at evaluation 
OR
 Any non-study treatment of curative intent of intra-anal and/or peri-anal HSIL

Table 4: Definition of Responder and Non-responder for Viral Clearance Endpoint

Responder	Non-Responder
No evidence of HPV-16 or HPV-18 in tissue/swab at evaluation 
AND
 No non-study treatment of curative intent of intra-anal and/or peri-anal HSIL	Evidence of HPV-16 or HPV-18 in tissue/swab at evaluation 
OR
 Any non-study treatment of curative intent of intra-anal and/or peri-anal HSIL

Table 5: Definition of Responder and Non-responder for Complete HSIL Regression Endpoint

Responder	Non-Responder
No histologic evidence of anal or anal/peri-anal HSIL or LSIL 
AND
 No non-study treatment of curative intent of intra-anal and/or peri-anal HSIL	Histologic evidence of anal or anal/peri-anal LSIL, HSIL or anal or anal/peri-anal carcinoma at evaluation 
OR
 Any non-study treatment of curative intent of intra-anal and/or peri-anal HSIL

Table 6: Definition of Responder and Non-responder for Disease Non-Progression Endpoint

Responder	Non-Responder
No histologic evidence of a worsening anal or anal/peri-anal condition to anal or anal/peri-anal cancer relative to baseline	Histologic evidence of worsening of anal or anal/peri-anal condition to anal or anal/peri-anal cancer relative to baseline
AND	OR
No non-study treatment of curative intent of intra-anal and/or peri-anal HSIL	Any non-study treatment of curative intent of intra-anal and/or peri-anal HSIL

Table 7: Definition of Responder and Non Responder for Endpoint of Regression or Clearance

Responder	Non-Responder
No histologic evidence of anal or anal/peri-anal HSIL on histology	Histologic evidence of anal or anal/peri-anal HSIL on histology
OR	AND
No evidence of HPV-16 and/or HPV-18 intra-anal and/or peri-anal lesion tissue	Evidence of HPV-16/18 intra-anal and/or peri-anal lesion tissue
AND	OR
No non-study treatment of curative intent of intra-anal and/or peri-anal HSIL	Any non-study treatment of curative intent of intra-anal and/or peri-anal HSIL

Study Population:

Inclusion:

1. Must understand, agree and be able to comply with the requirements of the protocol and be able to provide voluntary consent to participate and sign an Informed Consent Form (ICF) prior to study-related activities;
2. Age 18 years and above;
3. Negative screening test for HIV-1/2^a within 30 days of Dose 1;
4. Confirmed anal or anal/peri-anal HPV-16 and/or HPV-18 infection at Screening by PCR from HSIL specimen;
5. Anal tissue (blocks only) provided to the Study Pathology Adjudication Committee (PAC) for diagnosis must be collected within 10 weeks of first dose of VGX-3100;
6. At least one anal or anal/peri-anal (AIN2/3 and/or PAIN2/PAIN3) lesion that is histologically-confirmed as HSIL by the PAC at Screening;
 - a. The lesion needs to be large enough to biopsy, but the biopsy (≥ 4 mm) should not remove the entire lesion in order to allow for continued lesion measurement while on the study;
7. Investigator judges the subject to be an appropriate candidate for histology collection procedures (i.e. excision or biopsy);
8. Female subjects, must meet one of the following criteria with respect to their reproductive capacity:
 - a. Post-menopausal as defined by spontaneous amenorrhea for more than 12 months or spontaneous amenorrhea for 6-12 months with FSH level >40 mIU/mL;
 - b. Surgically sterile due to absence of ovaries or due to bilateral tubal ligation/occlusion performed more than 3 months prior to Screening;
 - c. Subject agreement to avoid pregnancy for one month after last dose (Week 12 or Week 40);
 - d. Women of Child Bearing Potential (WOCBP) are willing to use a contraceptive method with a failure rate of less than 1% per year when used consistently and correctly from Screening until one month following the last dose of investigational product (Week 12 or Week 40). The following are acceptable methods:
 - i. Hormonal contraception: either combined progestin-alone including oral contraceptive, injectable, implants, vaginal ring, or percutaneous patches. Hormonal contraceptives must not be used in subjects with a history of hypercoagulability (e.g. deep vein thrombosis, pulmonary embolism);
 - ii. Abstinence from penile-vaginal intercourse when this is the subject's preferred and usual lifestyle;
 - iii. Intrauterine device or intrauterine system;
 - iv. Male partner sterilization at least 6 months prior to the female subject's entry into the study, and this male is the sole partner for that subject;
9. Men who would father a child must agree to use at least one form of birth control during or continued abstinence from heterosexual intercourse prior to the study, for the duration of study participation and one month after completion of VGX-3100 administration;
10. Normal Screening electrocardiogram (ECG) or Screening ECG with no clinically significant findings as judged by the Investigator

^a An HIV rapid test may be used given the following conditions are met: 1. The test is an antigen/antibody immunoassay, 2. The test is only done using blood, 3. The test must be performed in the office and done by qualified study staff members

Exclusion:

1. Untreated micro invasive cancer^a;
2. Biopsy-proven Vaginal Intraepithelial Neoplasia (VAIN) and are not undergoing medical care and/or treatment for VAIN^b;
3. Biopsy-proven Vulvar Intraepithelial Neoplasia (VIN) and are not undergoing medical care and/or treatment for VIN^b;
4. Biopsy-proven Cervical Intraepithelial Neoplasia (CIN) 2/3 and are not undergoing medical care and/or treatment for CIN^b;
5. Biopsy-proven Penile Intraepithelial Neoplasia (PIN) and are not undergoing medical care and/or treatment for PIN^b;
6. Anal or anal/peri-anal HSIL that is not accessible for sampling by biopsy instrument;
7. Intra-anal and/or peri-anal lesion(s) that cannot be fully visualized at Screening;
8. Inability to have complete and satisfactory high resolution anoscopic exams (HRAs) as defined by full visualization of the anus, entire anal canal from the squamocolumnar junction at the border of the distal rectum, anal transformation zone, distal canal, anal verge, perianus;
9. Any treatment for anal or anal/peri-anal HSIL (e.g. surgery) within 4 weeks of Screening;
10. Pregnant, breast feeding or considering becoming pregnant within one month following the last dose of VGX-3100;
11. Presence of any abnormal clinical laboratory values greater than Grade 1 per Common Toxicity Criteria for Adverse Events (CTCAE) v4.03 within 45 days prior to Day 0 or less than Grade 1 but deemed clinically significant by the Investigator^c;
12. Immunosuppression as a result of underlying illness or treatment including:
 - a. Any prior history of other clinically significant immunosuppressive or clinically diagnosed Autoimmune disease;
 - b. Any primary immunodeficiency;
 - c. Long-term use (≥ 7 days) or oral or parenteral glucocorticoids at a dose of ≥ 20 mg/day of prednisone equivalent (use of inhaled, otic, nasal, topical, and ophthalmic corticosteroids are allowed);
 - d. Current or anticipated use of disease modifying doses of anti-rheumatic drugs (e.g. azathioprine, cyclophosphamide, cyclosporine, methotrexate) and biologic disease modifying drugs such as TNF- α inhibitors (e.g. infliximab, adalimumab, or etanercept);
 - e. Prior chemotherapy within 1 year;
 - f. History of solid organ or bone marrow transplantation;
13. History of previous therapeutic HPV vaccination (however, licensed prophylactic HPV vaccines are allowed, e.g. Gardasil[®]9, Gardasil[®], Cervarix[®]);
14. Receipt of any non-study related non-live vaccine within 2 weeks before or after any VGX-3100 dose;
15. Receipt of any non-study related live vaccine (e.g. measles vaccine) within 4 weeks before or after any VGX-3100 dose;
16. Significant acute or chronic medical illness that could be negatively impacted by the electroporation treatment as deemed by the Investigator;
17. Current or history of clinically significant, medically unstable disease which, in the judgment of the Investigator, would jeopardize the safety of the subject, interfere with the study results (e.g. chronic renal failure, angina, myocardial ischemia or infarctation, class 3 or higher congestive heart failure, cardiomyopathy, or clinically significant arrhythmias);

^a This criterion includes subjects who have microscopic or gross evidence of invasive cancer, or the suspicion of cancer in any histopathologic specimen by any pathologist at screening.

^b When observation is the standard of care this will not exclude a subject from the study.

^c If the lab is redrawn and the result from the redrawn sample no longer meets this exclusion criteria, then the subject is not excluded on the basis of this criterion

18. Treatment for non-anogenital malignancy within 2 years of Screening, with the exception of superficial skin cancers that only require local excision;
19. Bleeding or clotting disorder or use of blood thinners (e.g. anticoagulants or antiplatelet drugs) that would contraindicate IM injections within 2 weeks of Day 0;
20. History of seizures unless seizure free for 5 years with the use of one or fewer antiepileptic agents;
21. Sustained, manually confirmed, sitting systolic blood pressure >150 mm Hg or <90 mm Hg or a diastolic blood pressure >95 mm Hg at Screening or Day 0;
22. Resting heart rate <50 bpm (unless attributable to athletic conditioning) or >100 bpm at Screening or Day 0;
23. Prior major surgery within 4 weeks of Day 0;
24. Participated in an interventional study with an investigational compound or device within 4 weeks of signing informed consent form (participating in an observational study is permitted);
25. Less than two acceptable sites available for IM injection considering the deltoid and anterolateral quadriceps muscles;
 - a. Tattoos, keloids or hypertrophic scars located within 2 cm of intended treatment site;
 - b. Cardioverter-defibrillator or pacemaker on the ipsilateral side (to prevent a life-threatening arrhythmia) (unless deemed acceptable by a cardiologist);
 - c. Metal implants or implantable medical device within the intended treatment site (i.e. electroporation area);
26. Any illness or condition that in the opinion of the Investigator may affect the safety of the subject or evaluation of any study product;
27. Vulnerable Populations:
 - a. Drug (i.e. prescription or illicit) or alcohol use or dependence that, in the opinion of the Investigator, would interfere with adherence to study requirements;
 - b. Prisoner or subject who is compulsorily detained (involuntarily incarcerated) for treatment of either a psychiatric or physical (i.e. infectious disease) illness;
 - c. Active military personnel;
 - d. Study-related staff or family members of study-related staff

TRIAL SCHEDULE OF EVENTS

Table 8: Schedule of Events

Study Action	Screen (-10 wk. to -1d)	Day 0	8-14 days post dose 1 Phone Call	Week 4 (± 4 days)	8-14 days post dose 2 Phone Call	Week 12 (± 4 days)	Week 15 (± 1 Week)	Week 28 (± 1 Week)	Week 36 (± 1 Week)	Week 40 (± 1 Week)	8-14 days post dose 4 Phone Call	Week 64 (± 2 Weeks)	Week 88 (± 2 Weeks)
Informed consent	X												
Medical History/Demographics	X												
Medications (prior/concomitant)	X	X		X		X	X	X	X	X		X	X
Socio-behavioral assessment	X								X			X ⁿ	X
Inclusion/Exclusion criteria ¹	X	X											
Physical exam (PE)/assessment ^a	X	X		X		X	X	X	X	X		X	X
Vital signs	X ^b	X		X		X	X	X	X	X		X	X
Screening safety (12 lead ECG, laboratories) ^c	X												
Pregnancy Testing ^d	X	X		X		X	X	X	X	X		X	X
HIV Ab by ELISA	X								X				
Blood immunologic samples	X ^e	X ^e					X ^f		X ^e				X ^e
Oropharyngeal (OP) rinse		X		X			X	X	X			X	X
Vaginal, cervical, and penile swab		X		X			X	X	X			X	X
Intra-anal and/or peri-anal swab	X	X		X			X	X	X			X	X
Digital Anal Rectal Examination DARE ^g	X	X		X			X	X	X			X	X
High Resolution Anoscopy (HRA) ^h	X	X		X			X	X	X			X	X
Lesion photography ⁱ	X	X		X			X	X	X			X	X
Biopsy ^j	X								X			X ^q	
Inject VGX-3100 +EP ^k		X		X		X				X ^k			
Post treatment reaction assessment		X		X		X				X			
Distribute Participant Diary Card (PDC)		X		X		X				X			
Review PDC ^l			X		X		X				X	X	
Patient Reported Outcomes (PROs) (SF-36v2 TM) (EQ-5D-5L) ^m		X ^o	X	X	X	X	X		X	X	X ^p	X	X

¹ Subject eligibility will be reconfirmed at every visit.

- ^a Full Physical exam (PE) mandatory at Screening and study discharge (Week 88), otherwise targeted PE as determined by the Investigator or per subject complaints unless signs or symptoms dictate the need for a full PE.
- ^b Screening vital signs must include a measured height and weight and calculated body mass index (BMI) (Bodyweight in kilograms divided by height in meters squared). Weight will be collected at all dosing visits.
- ^c Screening 12-lead Electrocardiogram (ECG), complete blood count (CBC), serum electrolytes, blood urea nitrogen (BUN), creatinine (Cr), glucose, alanine aminotransferase (ALT), and Creatine Phosphokinase (CPK) performed within 45 days prior to first dose administration.
- ^d Negative spot urine pregnancy test is required for female subjects at Screening, prior to each study treatment, high-resolution anoscopy (HRA), and biopsy/surgical excision; the pregnancy test at Week 40 would only be needed for subjects who receive an additional dose.
- ^e At least 34 mL (4 x 8.5 mL yellow (ACD) tubes) whole blood and 4 mL serum per time point. At least 68 mL whole blood and 8 mL serum should be collected prior to first dose.
- ^f At least 51 mL (6 x 8.5 mL yellow (ACD) tubes) whole blood and 4 mL serum should be collected at Week 15.
- ^g Digital Anal Rectal Examinations (DARE) are to be performed once cytology has been collected and prior to HRA.
- ^h An additional visit may be scheduled to perform HRA if worsening of disease is suspected. Biopsies should not be performed at any visit other than at entry (Screening) and Weeks 36 and 64 for Subgroup C unless the Investigator suspects invasive cancer. All biopsy samples and/or excision samples must be sent to the Pathology Adjudication Committee (PAC) for review.
- ⁱ Photography of qualifying lesion(s) must be performed prior to and after biopsy, and at all HRA examinations. If a pre-biopsy digital photograph is not available for a historical biopsy sample at Screening, a post biopsy photo will be sufficient. Photographs of intra-anal lesion(s) will be for documentation purposes only. All qualifying peri-anal lesion(s) will be assessed using the ruler provided. The ruler should be placed in the field of vision and should be documented with photography at Screening, Day 0, and Weeks 4, 15, 28, 36, 64, and 88.
- ^j Tissue specimen (paraffin blocks) from all excised tissue lesion(s) that led to eligibility at study entry must be reviewed by the PAC and residual tissue from entry and Weeks 36 and 64 specimen(s) (paraffin blocks) must be sent to the central laboratory for immune analysis and Human Papillomavirus (HPV) testing.
- ^k Potential dosing at Week 40 is applicable for partial responders only.
- ^l A phone call will be used to review the Participant Diary Card (PDC) with subject within 8-14 days following doses 1 and 2. The subject will be expected to bring the PDC to the next visits for review. Subjects who receive an additional 4th dose will also have a phone call 8-14 days post dose 4 where the PDC will be reviewed. The subject should bring the PDC to the next visit.
- ^m Patient-reported outcome (PRO) measures (SF-36v2™ and EQ-5D-5L, plus two additional "global" questions will be assessed as described in Section 6.13.
- ⁿ This socio-behavioral assessment will only apply to those subjects in Subgroup C who receive a 4th dose of investigational product.
- ^o PROs at this time point must be administered prior to first dose of study drug.

^p PROs at this time point will only be for subjects who received a 4th dose of study drug.

^q Under Protocol Amendment 3.0, in addition to HSIL lesion(s) found at Screening, all visible lesions should have biopsy obtained at Week 64 and sent to the central pathology lab for review by PAC.

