4.3.2 CRITERIA FOR WITHDRAWAL FROM STUDY

Subjects who become ineligible to continue on the study based on no longer meeting the inclusion criteria should be discontinued from study treatment and managed per routine standard of care but should continue on the study without further biopsy.

Should a subject fail to attend the clinic for a required study visit, the site should attempt to contact the subject and reschedule the missed visit as soon as possible. The site should also counsel the subject on the importance of maintaining the assigned visit schedule for follow-up and treatment of anal or anal/peri-anal HSIL, and ascertain whether or not the subject wishes to and/or should continue in the study based on previous noncompliance. In cases where the subject does not return for the rescheduled visit or cannot be reached to reschedule the missed visit, the site should make every effort to regain contact with the subject (3 telephone calls to the subject should be made and if that fails, then a certified letter is sent to the subject's last known mailing address) so that they can be considered withdrawn from the study for disposition purposes. These contact attempts should be documented in the subject's medical record. Should the subject continue to be unreachable, then and only then will the subject be considered to have withdrawn from the study with a primary reason of "Lost to Follow-up." For all other subjects withdrawing from the study, an alternative reason for discontinuation should be recorded in the eCRF.

If a subject elects to discontinue treatment/EP they should be encouraged to stay in the study and complete all follow-up visits and procedures and have all scheduled immune assessment blood samples collected as indicated in the Schedule of Events ([Table 8](#)). At a minimum, the Investigator should make every effort to have the subject complete all assessments designated for the discharge visit (Week 88). A subject will be considered to have completed the study when he/she completes all scheduled study treatments and follow-up visits.

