6.19 ANAL PHOTOGRAPHS AND BIOPSIES

Eligible subjects are enrolled in the study based on the diagnosis of anal or anal/peri-anal HSIL confirmed by the PAC at Screening. Subjects will undergo HRA at Screening, Day 0, and at Weeks 4, 15, 28, 36, 64, and 88 to identify all intra-anal lesion(s). All intra-anal and/or peri-anal lesion(s) of adequate size (≥ 4 mm) will be biopsied at Screening. Once the PAC confirms HSIL at Screening, the Week 36 and 64 biopsies will be obtained from all HSIL site(s) confirmed by the PAC at Screening, unless the Investigator suspects disease progression. Investigators should follow **Table 1: Minimally Required Procedure at each Biopsy Visit for the Weeks 36 and 64 biopsies.** Under the Protocol 3.0 Amendment, in addition to HSIL lesion(s) found at Screening, all visible lesions should have biopsy obtained at Week 64 and sent to the central pathology lab for review by PAC. Photography of all qualifying intra-anal and/or peri-anal lesion(s) must be performed prior to and after biopsy, and at all HRA examinations. If a pre-biopsy digital photograph is not available for a historical biopsy sample at Screening, a post biopsy photo will be sufficient. Photographs of intra-anal lesion(s) will be for documentation purposes only. All qualifying peri-anal lesion(s) will be assessed using the ruler provided. The ruler should be placed in the field of vision and should be documented with photography at Screening, Day 0, and Weeks 4, 15, 28, 36, 64, and 88.

If the intra-anal and/or peri-anal tissue sample(s) result suggests progression to cancer, the Investigator may schedule an ad hoc visit to perform HRA and possible biopsy if clinically indicated.

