8.4 ANALYTICAL POPULATIONS

Analysis populations are:

- The modified intention to treat (mITT) population includes all subjects who receive at least one dose of Study Treatment. Analysis of the mITT population will be primary for the analysis of efficacy in this study.
- The per-protocol (PP) population comprises subjects who receive all doses of Study Treatment and have no protocol violations. Analyses on the PP population will be considered supportive of the corresponding mITT population for the analysis of efficacy. Subjects excluded from the PP population will be identified and documented prior to locking of the study database.
- The safety analysis set includes all subjects who receive at least one dose of Study Treatment.

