8.5 DESCRIPTION OF STATISTICAL METHODS

8.5.1 PRIMARY ANALYSES

The true treatment effect on the primary endpoint is p , where p denotes the true population probability of the primary endpoint. The primary hypothesis of superiority is: $H_0: p \leq 0.15$ vs. $H_1: p > 0.15$.

A p-value for this hypothesis test and corresponding 95% confidence interval will be computed based on the exact method of Clopper-Pearson. Superiority will be concluded if the one-sided p-value is <0.05 and the corresponding lower bound of the one-sided 95% CI exceeds 0.15.

For the analysis, the efficacy time frame is defined by any time starting from 14 days prior to the specified visit week.

The endpoint will be analyzed in two ways: a) based on all lesions and b) based on qualifying and new lesions.

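### A dosed subject whose lesions grow can go without both treatment and the Week 36 biopsy, and the protocol has no rule for counting that subject

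*Protocol*

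**What the plan says.** References are to version 3.0 of the protocol.

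**The scheduled biopsy.** The Synopsis (Study Design) and Section 6.3.8 plan the Week 36 biopsy without exception. Section 8.2 bases the primary endpoint on that tissue, and the Synopsis says that visual and digital examination alone cannot establish regression.

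**Rules that stop it.**
- Worsening at any time is "defined as any increase in lesion(s) area from baseline or worsening of anal or anal/peri-anal HSIL to cancer" (Synopsis, Study Design). Standard of care is then permitted, not required, and the subject "will continue on the study through Week 88 with HRA, but without further biopsy unless it is part of the standard of care".
- Under Section 4.3.2 a subject who no longer meets the inclusion criteria stops study treatment and is "managed per routine standard of care but should continue on the study without further biopsy". A later paragraph of the same section encourages a subject who elects to stop treatment to "complete all follow-up visits and procedures".
- The Synopsis (Efficacy Assessment) and Sections 3.0, 3.7, 6.17 and 6.19 qualify the Week 36 biopsies with an exception where the investigator suspects progression.
- Footnote h to Table 8 limits biopsy outside the planned visits to suspected invasive cancer. Sections 6.20 and 7.1 allow it for suspected progression.

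**Rules for counting.** Table 2 makes a subject a non-responder on histology (HSIL, AIS or carcinoma), on positive tissue PCR, or on non-study treatment of curative intent. Section 7.1 adds anyone with an unscheduled biopsy. The primary population, mITT, "includes all subjects who receive at least one dose of Study Treatment" (Section 8.4). Section 8.5.8 imputes nothing beyond adverse event dates. Section 8.6 assumes that 90% are evaluable at Week 36. Section 8.5.1 tests against 0.15: "Superiority will be concluded if the one-sided p-value is <0.05".

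**The concern.** The endpoint exists only if Week 36 tissue exists, and one of the rules that stops its collection is triggered by a bad course. A subject whose lesions have grown is a likely failure. If that subject has neither treatment nor biopsy and drops out of the denominator, the observed response rate rises. In a single-arm trial against a fixed 15% there is no control group in which the same selection would offset it. Tissue that was not taken cannot be recovered by any later analysis plan, so the collection rule has to be settled in the protocol.

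**Working it through.** **1. The plan's own figure.** Inputs from Sections 8.5.1 and 8.6: null rate 0.15, assumed rate 0.40, exact binomial test, one-sided 0.05, 24 subjects, 90% evaluable.

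24 × 0.9 = 21.6, taken as 21. The smallest r with P(X ≥ r | 21, 0.15) < 0.05 is 7 (0.0287), and P(X ≥ 7 | 21, 0.40) = 0.7998. The stated power of about 80% reproduces with 21 in the denominator.

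Two alternatives keep all 24 in the denominator, where r = 8 and the size is 0.0199:
- No loss, or losses only among true failures (rate stays 0.40): power 0.808.
- 10% lost regardless of outcome and counted as failures (rate 0.9 × 0.40 = 0.36): power 0.680.

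So the sample-size statement fits best with unevaluable subjects leaving the denominator, but it does not prove that they do.

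**2. Following a worsened subject through the rules.**

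| Course before Week 36 | Classified by |
|---|---|
| Curative-intent treatment given | Table 2: non-responder |
| Carcinoma | Table 2: non-responder |
| Unscheduled biopsy | Section 7.1: non-responder |
| Lesion area up, no treatment, no biopsy | No rule |

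The last row cannot be a responder, because the responder column needs tissue findings, and it meets none of the non-responder conditions. A subject who loses eligibility with neither treatment nor biopsy is in the same position.

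**3. Effect of the denominator.** Exact P(X ≥ x | n, 0.15) and one-sided 95% Clopper-Pearson lower bound:

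| Responders / n | p | Lower bound | Result |
|---|---|---|---|
| 7/24 | 0.0572 | 0.1457 | fails |
| 7/23 | 0.0463 | 0.1525 | passes |
| 7/22 | 0.0368 | 0.1599 | passes |
| 7/21 | 0.0287 | 0.1682 | passes |
| 6/24 | 0.139 | 0.115 | fails |
| 6/18 | 0.042 | 0.156 | passes |

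**4. Type I error.** Assumption, not in the documents: a fraction q of true non-responders has no tissue and is excluded. The number excluded is Bin(24, (1 − p)q). Among the n that remain, responders are Bin(n, p / (1 − (1 − p)q)), tested at the critical value for n (8 at n = 24, 7 at n = 19 to 23, 6 at n = 18). At p = 0.15:

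| q | Expected excluded, 24 × 0.85 × q | Apparent rate, 0.15 / (1 − 0.85q) | Type I error |
|---|---|---|---|
| 0 | 0 | 0.150 | 0.020 |
| 0.10 | 2.0 | 0.164 | 0.051 |
| 0.20 | 4.1 | 0.181 | 0.068 |
| 0.30 | 6.1 | 0.201 | 0.100 |

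Part of the first step is discreteness: the critical value falls from 8 to 7, and an unselected sample of 23 already has size 0.046. The excess over 0.05 is therefore marginal at q = 0.10 and clear at 0.20 and above.

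**The case against.** **The worsening sentence has a milder reading.** It can be taken to stop biopsy only for those who receive standard of care, as the Subgroup C sentences do. On that reading this gap closes, provided the treatment is of curative intent. This stands as a possible reading. But the Subgroup C text ties the loss of biopsy to an explicit choice to treat, while the worsening sentence ties it to worsening and merely permits treatment. Sites could follow either.

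**A reader might infer that everyone who worsens escapes Table 2.** The documents do not support that. Treated subjects, carcinomas and subjects with an unscheduled biopsy are all non-responders already, and standard-of-care tissue goes to the adjudication committee. Only the untreated, unbiopsied subject is left.

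**A reader might infer that loss of eligibility also selects subjects doing badly.** It need not. Most inclusion criteria are fixed at Screening, and a lapse in one such as contraception says nothing about the lesion. That rule is a contradiction within Section 4.3.2 and a rare, avoidable loss of data. The directional bias rests on the worsening rule.

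**A reader might also infer that ruler error would trigger the rule in most stable subjects.** The definition has no margin, but the protocol gives no measurement error, and a reading above baseline is not the same as a lost biopsy. No size can be put on this.

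**Section 8.4 puts no evaluability condition on mITT**, so 24 may be the intended denominator. That is fair, but the text gives the subject no outcome within the 24, and the sample-size assumption points the other way. Handling of missing outcomes in general can be left to an analysis plan. The conflicting biopsy instructions, and a responder definition that omits a course which the protocol itself creates, cannot.

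**Conclusion.** The point holds in a limited form. The protocol conflicts with itself on whether worsening or loss of eligibility ends the scheduled Week 36 biopsy. A dosed subject who worsens by area and has neither treatment nor biopsy is unclassified in the primary analysis. If such subjects are excluded, the bias is upward. One exclusion is enough to turn failure into success when there are exactly seven responders, and losing 20% of non-responders would give a type I error of 0.068.

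This rests on three things: the literal reading of the worsening sentence, exclusion from the denominator (suggested by Section 8.6 but not stated), and an assumed number of affected subjects, which the documents do not give and which may be small.

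**What to change.** (a) Reconcile the worsening paragraph of the Synopsis, both paragraphs of Section 4.3.2, the suspected-progression exceptions (Synopsis Efficacy Assessment and Sections 3.0, 3.7, 6.17 and 6.19) and footnote h to Table 8 with the Week 36 schedule in the Synopsis and Section 6.3.8. The text should say once whether worsening or loss of eligibility alone ends the scheduled biopsy. Which way that goes is a clinical decision for the sponsor and investigators.

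(b) Whatever is decided, add to the non-responder column of Table 2, and to Sections 7.1 and 8.5.1, that a dosed subject who met the worsening definition and has no Week 36 tissue counts as a non-responder and stays in the mITT denominator.

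The cost is wording only; (b) adds no procedure. The response rate may look slightly less favourable. With all 24 in the denominator, power stays at 0.808 if the subjects so counted are true failures. It would fall to 0.680 only if 10% of all dosed subjects were counted as failures regardless of their true outcome.
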